9.2. Sample Size

[figure not shown]
The recruitment goal for the Toffee Full Face product validation will be 45 participants.

[figure not shown]
For each requirement challenged by the product validation, the outcome for each participant will be recorded as a pass or fail. Therefore, in order to evaluate the validation criteria, the analysis will be performed using a 95% confidence interval for the proportion of successes, where the lower confidence limit must be greater than the proportion pre-defined for each validation requirement.

The statistical power of this one-proportion test, i.e. the probability of not making a type II error, is determined by the sample size. To estimate an adequate sample size to achieve 80% power, the Minitab power and sample size tool was used. Data from the most recent clinical trial (TR-32203) was used as an estimate for the population proportion, this was recalculated at the test report stage with the actual proportion found, in order to confirm its validity. Where there was no comparable data from the past clinical trial, data from previous validation trials of recent products was leveraged. Formal calculation by validation requirement are present in TP-2163 but are not required to present individually here in this CIP. From the calculations, a sample size of 40 has been determined as the minimum sample size for 95% confidence across all requirements. Therefore, the recruitment goal for the Toffee Full face product

validation will be 45 participants to ensure that at least 40 participants complete the clinical investigation accounting for potential dropouts.

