9.1. Statistical Design

Next, the following data analysis strategy will be employed.

1. For each participant and requirement, it will be determined if the requirement is met by the participants' response(s) to associated questions.
2. Minitab will be used to perform a one-sided one-proportion test on each requirement using the confidence limit to confirm that the acceptance criteria has been met:

H_0 : proportion = Reliability Limit
 H_1 : proportion > Reliability Limit
Acceptance criteria:
 $P \leq 0.05$ to reject H_0

FPH as the sponsor may consult an external statistician to assist with or review the analysis of the data.

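### Does section 9.2 justify n = 40 by observed power, and does it mistake confidence for power?

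*Combined protocol and SAP*

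**What the plan says.** Section 9.1 sets the decision rule. The sponsor will "perform a one-sided one-proportion test on each requirement", "using the confidence limit to confirm that the acceptance criteria has been met", and rejects the null hypothesis when P is at most 0.05.

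Section 9.2 says what the sample size is for: "The statistical power of this one-proportion test, i.e. the probability of not making a type II error, is determined by the sample size". It gives the target: "To estimate an adequate sample size to achieve 80% power, the Minitab power and sample size tool was used". The assumed proportions come from TR-32203, or from validation trials of other recent products where TR-32203 has nothing comparable. On the TR-32203 estimate the text adds that "this was recalculated at the test report stage with the actual proportion found, in order to confirm its validity". The calculations for each requirement are said to be in TP-2163. The section concludes that "a sample size of 40 has been determined as the minimum sample size for 95% confidence across all requirements", and sets recruitment at 45 to allow for dropouts.

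**The concern.** Two things look wrong.

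- **The recalculation.** An estimate is set against an actual proportion found, and the comparison is said to confirm validity. That can be read as a plan to recompute power from this trial's own result. With n and the limit fixed, such power depends only on the success count, which also gives the P value, so it is no separate evidence on whether the sample was large enough. A report that used it could excuse a failed requirement as underpowered, or cast doubt on a valid narrow pass.
- **The label on n = 40.** Confidence is set by the 0.05 criterion in section 9.1, while n sets power. Calling 40 the minimum for 95% confidence names a property that the calculation did not target, and the concluding sentence does not repeat that 80% power was reached for every requirement.

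**Working it through.** **Inputs.** From section 9.1: one-sided test, 0.05. From section 9.2: 80% power, n = 40, recruitment 45. The limits (p0) and planning proportions (p1) are not visible and may be in withheld text, so the values below are assumptions.

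**The plan's figure.** n = 40 cannot be reproduced without p0 and p1. It can be inverted with the usual formula, n = ((1.645·√(p0(1−p0)) + 0.842·√(p1(1−p1))) / (p1−p0))². Forty participants give 80% power for p0/p1 pairs of about 0.70/0.86, 0.75/0.90, 0.80/0.94 and 0.85/0.97, so 40 is attainable. The recruitment figure also fits: 40/0.90 = 44.4 and 40/0.89 = 44.9 both round up to 45.

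**If power were recomputed from this trial's result.** Let r be the smallest count with P(X ≥ r | 40, p0) ≤ 0.05. Observed power at count x is P(X ≥ r | 40, x/40). Exact binomial:

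| Assumed limit | Smallest passing count r | Observed power at r | Observed power at r − 1 |
|---|---|---|---|
| 70% | 34 | 0.607 | 0.435 |
| 75% | 35 | 0.616 | 0.433 |
| 80% | 37 | 0.647 | 0.423 |
| 85% | 38 | 0.677 | 0.414 |
| 88% | 39 | 0.736 | 0.399 |
| 90% | 40 | 1.000 | 0.363 |

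At a limit of 80% the P values are 0.076 for 36/40, 0.028 for 37/40 and 0.008 for 38/40, and the observed powers are 0.42, 0.65 and 0.86. The formula above turns the same results into required sample sizes of 83, 50 and 32. The figure follows the result, so on this reading the step would confirm nothing.

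**Whether the text says this.** The charge needs two steps.

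1. *The proportion must be this trial's.* The clause is in the past tense and directly follows the mention of TR-32203, while sections 9.1 and 9.2 put this trial's analysis in the future tense. Section 9.5 calls this trial's report the final investigation report; section 9.2 speaks of a test report stage. Updating a planning value with the completed earlier trial's proportion is legitimate.
2. *Power must be what is recalculated.* The nearest antecedent is the estimate of the population proportion. Comparing a planned with an observed proportion is an ordinary descriptive check.

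The text establishes neither step.

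**Confidence against power.** Exact confidence is 1 − P(X ≥ r | n, p0); power is P(X ≥ r | n, p1).

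| Assumed limit | Confidence, n = 20 | Confidence, n = 40 | Assumed true proportion | Power, n = 20 | Power, n = 40 |
|---|---|---|---|---|---|
| 70% | 0.965 | 0.976 | 90% | 0.68 | 0.90 |
| 75% | 0.976 | 0.957 | 90% | 0.39 | 0.79 |
| 80% | 0.988 | 0.972 | 95% | 0.36 | 0.86 |
| 85% | 0.961 | 0.951 | 97% | 0.54 | 0.88 |

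At these limits, 95% confidence is already met with 20 participants, and power is what improves with 40. The label is therefore imprecise. At higher limits n does govern whether a 95% lower bound can pass at all: with no failures the bound is 0.05^(1/n), which is 0.861 at n = 20 and 0.928 at n = 40. But section 9.2 describes a power calculation, not a zero-failure plan.

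**The case for a change.** The best case for a change is that section 9.2 is the only visible justification of the sample size, with the detail left to TP-2163. Its conclusion names the wrong property, and its validity check is either unidentified or, on one reading, uninformative. Rewording two sentences would cost almost nothing and would close off a poor argument in the final report.

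Part of this stands. The recalculation sentence does not say which trial, which report or which quantity it means. The concluding sentence would be more exact if it named 80% power at one-sided 0.05. The arithmetic on observed power is also right.

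The suggested harm does not stand. The section says that sample size determines power, names the 80% target, and derives 40 from those calculations, so a statistician will read 95% confidence as the error level used in them. The observed-power figures apply only if both unproven steps are granted and the limits are as assumed. Even then, the recalculation has no role in the rule of section 9.1, which decides every requirement by the one-sided test against its limit.

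**Conclusion.** No change to the plan is called for. The section has an unclear antecedent and a loose label, both clerical. On the readings that fit its tense and position, the recalculation is either a legitimate update from the earlier trial or a descriptive comparison. The label abbreviates 80% power at 95% confidence.

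The effect on the trial is nil: the test, the 0.05 criterion, the limits, n = 40, recruitment of 45 and every pass or fail result stay as they are. This rests on the visible text. The limits, the planning proportions and TP-2163 could not be seen, so n = 40 is neither confirmed nor shown to be wrong. Only if the final report argued adequacy from power recomputed on this trial's own proportion would there be something to object to, and the plan does not clearly commit to that.

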7.10. Participant Procedure

[figure not shown]
[REDACTED]

[REDACTED]

[Redacted]

[Redacted]	[Redacted]	[Redacted]
[Redacted]	[Redacted]	[Redacted]

Additionally, the PI may withdraw a participant at any time for the following reasons:

- Protocol violation
- Safety concerns
- Serious illness
- AE/SAE

The reason for participant discontinuation in the clinical trial is to be recorded in the CRF.

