7.13. Foreseeable Complications

From the Manufacturer and User Facility Device Experience database, the common reported injuries from PAP therapy and associated interface use are pressure sores, leading to cuts, rashes, and skin abrasions and breakdown. Allergic reaction to materials in the interface can occur. Common complaints are discomfort and soreness on the areas of contact with the interface. Participants on the clinical trial are informed that they can switch back to their usual mask if required. In instances of malfunction or damage, the investigational product and its components may be replaced, as recorded in the CRF.

8. Clinical Trial Documentation

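### As far as they are visible, the scoring and exclusion rules can drop participants who gave up on the mask from the denominator of the continued-delivery endpoint

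*Combined protocol and SAP*

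**What the plan says.** - **Endpoint.** The primary endpoint in 7.4 is that the mask supports continued delivery of PAP therapy in the home. Comfort and adequate performance, with minimal leak as the example, are secondary endpoints.
- **Scoring.** For each participant, 9.1 determines whether the "requirement is met by the participants' response(s) to associated questions". Section 9.2 adds that every participant's outcome on each requirement is recorded as pass or fail.
- **Test.** "Minitab will be used to perform a one-sided one-proportion test on each requirement using the confidence limit", with success declared at a p-value of 0.05 or less. Section 9.2 words the same criterion as an interval, "where the lower confidence limit must be greater than the proportion pre-defined for each validation requirement". The Reliability Limits are not given in the visible text.
- **Dropout.** Section 9.2 sets 40 as the minimum and recruits 45 "to ensure that at least 40 participants complete the clinical investigation accounting for potential dropouts".
- **Analysis set.** Section 9.6 includes everyone who consented, was fitted and used the mask at home, unless there is a clear reason for exclusion. Its example of such a reason is conclusive evidence that another mask was worn in the intervention period. Exclusions must be documented with the reason.
- **Stopping.** The withdrawal text after 7.10 lists safety concerns and AE/SAE among the reasons for withdrawal by the PI, and states: "The reason for participant discontinuation in the clinical trial is to be recorded in the CRF". Section 7.13 says "Common complaints are discomfort and soreness on the areas of contact with the interface" and that participants are told they may go back to the mask they normally use.

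**The concern.** A person who stops using the mask because it hurts, damages the skin or leaks is direct evidence against an endpoint about continued delivery. Two visible rules can take that person out of the count:

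1. Under 9.1 the score comes from answers. Section 9.6 may include a participant who left before answering, but without a rule that assigns a value there is nothing to enter in a one-proportion test.
2. Under 9.6, a participant who used the option in 7.13 and returned to the usual mask has worn a different mask in the intervention period, which is the plan's own example of a ground for exclusion.

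Both routes act mainly on people who did badly on the mask. Losing them lowers the denominator without lowering the number of passes, so the proportion rises. The trial is open-label and the sponsor and investigator belong to the same company. A scoring choice left open until the data are seen would therefore be hard to defend.

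**Working it through.** **1. The plan's own figures.** The implied dropout allowance is 5/45 = 11.1%, and 40/(1 − 0.111) = 45; a 10% rate also rounds up to 45. The step from 40 to 45 is sound. The 40 itself can be neither confirmed nor refuted, because neither the limits nor the assumed proportions are visible. At one-sided 0.05 and 80% power, n = [(1.645·√(p0(1−p0)) + 0.842·√(p1(1−p1)))/(p1−p0)]² gives about 40 for many pairs: 0.70 against 0.865 gives 40, 0.75 against 0.90 gives 42, and 0.80 against 0.94 gives 38.

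**2. Effect of the denominator.** Inputs: 40 completers and up to 5 leavers (9.2), one-sided 0.05 (9.1), and *assumed* limits p0. The exact p-value is P(X ≥ r) for X ~ Binomial(n, p0). The count r is the smallest that passes with n = 40; the numerator is then held fixed while leavers are added as fails.

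| Assumed limit | r of 40, p | one leaver failed (n = 41), p | five failed (n = 45), p | passes needed of 45 |
|---|---|---|---|---|
| 70% | 34, 0.024 | 0.046 | 0.26 | 37 |
| 80% | 37, 0.0285 | 0.066 | 0.44 | 41 |
| 85% | 38, 0.049 | 0.118 | 0.64 | 43 |
| 90% | 40, 0.015 | 0.074 | 0.71 | 45 |

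At 80%, 85% and 90% a single mask-related leaver reverses a result at the minimum passing count. At 70% it takes two (34/42, p = 0.080). Better results are more robust: 40/40 with five leavers failed is 40/45, which still passes at an assumed 70% (p = 0.003) or 75% (p = 0.018), but not at 80% (p = 0.090).

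**3. False-pass rate if only those who stay are scored.** Let the true success rate equal the limit p0. Of 45 participants, 5% of successes leave and a fraction f of failures leaves. Retention is R = 0.95·p0 + (1 − f)(1 − p0), and the success rate among those who stay is 0.95·p0/R. The number who stay is Binomial(45, R), and the exact test is applied to each possible number.

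Example with p0 = 0.80 and f = 0.25: R = 0.76 + 0.15 = 0.91; success rate among stayers 0.76/0.91 = 0.835; expected leavers 45 × 0.09 = 4.05; false-pass rate 8.3%.

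| f | 75% limit | 80% limit | 85% limit | expected leavers |
|---|---|---|---|---|
| 20% | 7.7% | 6.2% | 7.3% | 3.9, 3.6, 3.3 |
| 25% | 10% | 8.3% | 9.1% | 4.5, 4.1, 3.6 |
| 50% | 35% | 30% | 24% | 7.3, 6.3, 5.3 |

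The nominal rate is 5%. The first two rows fit within the plan's allowance of five leavers. The last exceeds it, clearly so at the 75% and 80% limits.

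**The case against.** A reader might infer more: that participants withdrawn because of the mask are not scored as failures, and that the test is a completers-only test. The documents do not say that.

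- Section 9.6 includes all fitted home users, and 9.2 speaks of a pass or fail for each participant. Both lean away from a completers-only set.
- Recruiting 45 for 40 is a sample-size allowance, compatible with any way of scoring dropouts.
- The natural places for a scoring rule are not shown. Section 9.3, on pass and fail criteria, is a bare heading; 7.7 and 7.8 are redacted; the withdrawal list follows redacted text and no 7.11 heading is visible; and 9.1 starts partway through its text. What is missing for that reason cannot be charged to the plan.
- Early leavers need not lack data. Questionnaire timing is redacted, the appendix contains a sleep diary, and eligibility requires a PAP device that records data.
- Not every withdrawal is a mask failure: protocol violation and serious illness are also listed. Nor is a mask-related stop a failure of endpoint 1 by definition, because its operational requirement is not visible.
- The different-mask exclusion has a reasonable purpose, since answers about another mask say nothing about this one.

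All of this stands against the stronger reading. It does not remove the conflict between two visible rules: 7.13 permits a switch back that 9.6 gives as a ground for exclusion, and neither says whether the reason for switching matters. Nor does inclusion under 9.6 supply a value where there are no answers.

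**Conclusion.** The point holds in limited form. The visible rules in 9.1, 9.6 and 7.13 can, if followed literally, take people who stopped or switched back because of the mask out of the primary endpoint's denominator. The bias would favour the mask. A rule elsewhere in the plan may already prevent this; if so, 9.1 and 9.6 need to agree with it.

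The size is uncertain. Every figure rests on assumed Reliability Limits. The reversals start from the minimum passing count and treat the added leavers as mask failures. With 20% to 25% of failures leaving, the false-pass rate is about 6% to 10% against a nominal 5%, a modest inflation. The 24% to 35% range needs half of all failures to leave, for which the documents give no basis, and should not be read as the expected effect. The change is worth making because a single reclassified participant can decide a borderline requirement in a sample of 40 to 45.

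**What to change.** 1. Reconcile 9.6 with 7.13, so that the different-mask exclusion does not remove a participant who used the mask at home and then switched back because of it.
2. State in 9.1 and 9.6 that a participant who used the mask at home and stopped or switched back for a mask-related reason recorded in the CRF (discomfort, skin effect, leak, fit, or a mask-related AE or safety concern) stays in the denominator and is scored a fail on endpoint 1 and on the requirement the reason concerns.
3. Leave unscored only discontinuations unrelated to the mask, such as relocation or unrelated illness, and list them with reasons.
4. Report a sensitivity result counting every leaver as a fail.
5. If 9.3 or another section not shown already has a scoring rule, bring 9.1 and 9.6 into line with it.

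The cost is wording. The discontinuation reason is already recorded in the CRF; the only addition is to make sure the reason for a switch back is recorded there too. No extra participants are needed. The reported proportions may come out slightly less favourable.

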9.3. Pass and Fail Criteria

9.4. Statistical Termination

No interim analysis will be conducted as statistical outcomes will not change the conduct of the clinical trial.

9.5. Statistical Procedure Deviations

Statistical procedure deviations will be reported to the PI and the sponsor. Deviations from the original statistical plan will be explained in the final investigation report.

9.6. Selection Criteria

All participants who consent and whom are fitted with the Toffee Full Face mask and use in home, will be included in the analysis unless clear reason for exclusion are present such as definitive proof of wearing a different mask during the intervention period. Any data points that are excluded will be documented clearly with the reason for their exclusion.

10. Data Management

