7.3. Equipment

7.4. Endpoints

Primary endpoint:

1. The Toffee Full Face mask facilitates the continued delivery of PAP therapy when used in the home

Secondary endpoints:

2. The Toffee Full Face mask, including the cushion and headgear, is comfortable when used for the delivery of PAP therapy in the home
3. The Toffee Full Face mask performs (e.g. minimal leak) adequately when used for the delivery of PAP therapy in the home
4. The Toffee Full Face mask is easy to disassemble/re-assemble when required for cleaning
5. The Toffee Full Face mask sizing guide is accurate in predicting the correct size for the participants

[REDACTED]

[REDACTED]

[REDACTED]

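### Section 9.6 lets use of another mask remove a participant from the analysis, so people who abandon the Toffee mask because of the mask can drop out of the primary endpoint's denominator and may bias its pass proportion upward

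*Combined protocol and SAP*

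**What the plan says.** Section 9.6 defines the analysis set. Participants who consent, are fitted with the mask and use it at home are "included in the analysis unless clear reason for exclusion are present such as definitive proof of wearing a different mask during the intervention period". This is the only example of a reason for exclusion, and it does not depend on why the other mask was worn. The section then adds: "Any data points that are excluded will be documented clearly with the reason for their exclusion".

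Section 7.13 lists skin injury and allergic reaction, then states: "Common complaints are discomfort and soreness on the areas of contact with the interface". Its next sentence is: "Participants on the clinical trial are informed that they can switch back to their usual mask if required".

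The primary endpoint in 7.4 is: "The Toffee Full Face mask facilitates the continued delivery of PAP therapy when used in the home". Section 9.1 says: "For each participant and requirement, it will be determined if the requirement is met", using answers to associated questions. It plans to "perform a one-sided one-proportion test on each requirement" against a reliability limit, rejecting at P ≤ 0.05. Section 9.2 confirms that "the outcome for each participant will be recorded as a pass or fail", requires the lower limit of a 95% interval to exceed the predefined proportion, and sets recruitment at 45 so that 40 complete. Section 7.2 states that there is no control group.

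**The concern.** A participant who stops using the Toffee mask because it hurts, and returns to the usual one, does what 7.13 permits and thereby creates the ground for exclusion named in 9.6. On a plain reading of endpoint 1 that person is a likely failure. The exclusion is therefore tied to something close to the outcome itself.

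The decision rests on one pass proportion set against a fixed limit, so no comparison arm can offset the loss of failures. If a good share of those excluded would have failed, the chance of declaring the primary requirement met when it is not rises above the nominal 5%. With about 45 participants, one or two such exclusions can decide a result near the limit.

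**Working it through.** **The plan's own figures.** The minimum of 40 cannot be reproduced, because the reliability limits and assumed true proportions are not in the visible text. Working backwards with the exact binomial (n=40, one-sided 5%, 80% power), the true pass rate would have to be 0.880, 0.943 or 0.962 for limits of 0.70, 0.80 or 0.85. The target of 45 fits a loss of one in nine: 40/(1 − 1/9) = 45. The sample size is not disputed here.

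**Inputs.** From the documents: N = 45 (9.2), a one-sided test at 0.05 (9.1) and a binary outcome (9.2). Assumed:
- limit p0 = 0.70, 0.80 or 0.85
- true pass rate among all 45 equal to p0
- share s of participants who switch, all of them excluded
- share g of switchers who would have failed.

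**Direction.** The pass rate among those kept is (p0 − s(1 − g))/(1 − s). This exceeds p0 when g > 1 − p0, that is, when g exceeds 0.30, 0.20 or 0.15. The shift can go the other way: excluding five people who would all have passed turns 41/45 = 91.1% into 36/40 = 90.0%.

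**False-pass rate.** The number excluded is x ~ Bin(45, s). Passes among those kept follow Bin(45 − x, kept rate), compared with the exact 5% critical value for that n. For example, p0 = 0.80, s = 0.10 and g = 0.5 give a kept rate of (0.80 − 0.05)/0.90 = 0.833. Summing over x gives a false-pass rate of 7.9%. With no exclusion the critical values at n = 45 are 37, 41 and 43 passes.

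| Switching s | Share failing g | p0 = 0.70 | p0 = 0.80 | p0 = 0.85 |
|---|---|---|---|---|
| no exclusion | – | 4.7% | 3.8% | 2.7% |
| 5% | 1 | 9.5% | 10.7% | 15.6% |
| 5% | 0.75 | 6.7% | 7.2% | 10.3% |
| 5% | 0.5 | 4.7% | 4.8% | 6.6% |
| 5% | 0.25 | 3.2% | 3.1% | 4.2% |
| 10% | 1 | 23.1% | 33.2% | 52.7% |
| 10% | 0.75 | 12.7% | 17.2% | 27.2% |
| 10% | 0.5 | 6.4% | 7.9% | 12.3% |
| 10% | 0.25 | 2.9% | 3.3% | 5.0% (0.0496) |

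The row with s = 10% and g = 1 is extreme: switchers would be s·g/(1 − p0) = 33%, 50% or 67% of all failures. The rate passes 5% only when g exceeds about 0.55/0.53/0.35 at s = 5%, or 0.42/0.36/0.25 at s = 10%.

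**Single results near the limit**, using P(X ≥ r | n, p0):
- p0 = 0.80: 40/45 gives p = 0.090 (not met); with one failure excluded, 40/44 gives p = 0.044 (met).
- p0 = 0.85: 42/45 gives p = 0.079; 42/44 gives p = 0.030.
- p0 = 0.70: two exclusions are needed; 36/45 gives p = 0.093, 36/43 gives p = 0.031.
- p0 = 0.80, three exclusions: 39/45 gives p = 0.18; 39/42 gives p = 0.021.

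**If the 95% interval in 9.2 is two-sided** (2.5% level), g = 0.5 gives 2.1/3.1/1.8% at s = 5% and 3.3/4.9/5.2% at s = 10%. The one- and two-exclusion reversals above would not pass at that level, but others would: at p0 = 0.80, 41/45 gives p = 0.038 and 41/44 gives p = 0.015.

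**The case against.** The strongest reply is that 9.6 is not aimed at these people. Its demand for definitive proof fits undisclosed non-adherence better than an open, permitted return to the usual mask, which could be handled as a discontinuation with its reason in the CRF. Neither section refers to the other. The second sentence of 9.6 speaks of data points, so only nights or answers recorded in another mask may be meant; the participant would then stay in the denominator and the bias would largely vanish. The content of 9.3, the scoring questions and most of the withdrawal text are not visible, and a rule scoring such participants as failures could sit there. Brief use of another mask need not be a failure. Every rate above is assumed, and at 2–3% switching with half failing the false-pass rate is only 3.9–4.7%.

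Much of this stands as a limit on size and certainty. It does not remove the point. The main sentence of 9.6 is about participants, and it draws no line by cause. Proof that another mask was worn says nothing about why. Documenting exclusions lets a reader recompute the result but leaves the failures outside the primary analysis. If 9.3 does score these participants as failures, the plan must still say which section prevails, because a person removed under 9.6 is not there to be scored.

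**Conclusion.** The concern holds and should be fixed, with moderate confidence. As written, 9.6 can take likely failures of endpoint 1 out of its denominator, and the pass proportion moves up whenever those excluded would pass less often than those kept. The actual size cannot be determined from the visible text. Under the assumed limits, with all switchers excluded, inflation ranges from none (few switchers, or few who would have failed) to false-pass rates of about 6–12% at 10% switching with half failing, and 13–27% with three quarters failing. The conclusion rests on reading 9.6 as excluding whole participants and on a mask-related return to the usual mask counting as a failure of endpoint 1. It covers that endpoint only.

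**What to change.** For endpoint 1, amend 9.6 as follows, unless 9.3 already has this effect and overrides 9.6:
- Keep every participant who was fitted with the mask and used it at home in the primary denominator.
- Count a return to the usual mask for a mask-related reason as not meeting the endpoint.
- Limit the exclusion to data generated in another mask, or to use of another mask for reasons unrelated to the Toffee mask.
- Report the present 9.6 set as a labelled sensitivity analysis, showing returns of unknown reason both as not met and as excluded.
- Reconcile 9.6 with 9.3 and 7.13. The permission in 7.13 is unchanged.

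The cost is a wording change and one extra analysis, and the reported pass proportion may be lower. The reason for each return to the usual mask must be recorded if the CRF does not already capture it; reasons for discontinuation and for excluded data are already required. Power for endpoint 1 should be rechecked, since these participants would count as fails and not as losses. At an assumed limit of 0.80 and n = 45, 41 passes are needed, so at most 45 − 41 = 4 fails are allowed.
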